The number of outbreaks per arm will be collected from VESUV. At the start of the evaluation period, we will ask participating hospitals to submit the number of full-time positions per included ward. The number of inpatients per ward per day will be obtained from NPR. The number of positions and inpatients will be used as denominators when estimating the secondary attack rate in outbreaks. The number of patients registered in NOIS will be compared to the number of daily inpatients registered in NPR. If the number of inpatients per day changes over time, we will make a new collection of the number of full-time positions to capture significant changes in the organization and size of included wards.

NOIS and NOIS-POSI are surveillance systems where numerators and denominators are registered. From these systems, it is sufficient to receive the results for each ward in the form of the proportion of patients with different types of infections.

From NPR, we will apply for data for all hospitalized patients at both intervention and control wards from and including 1. January 2020 up to the time of application in 2024, giving numerators and denominators for the periods before, during and after the intervention.

When comparing intervention and control groups, we will estimate relative risk (RR) and absolute risk difference (ARF) with 95% confidence intervals (table 2). We will report two-sided p-values where applicable and use the significance criterion p<0.05.

We will use modified Poisson regression to compare hand hygiene compliance one year after NOST was introduced in the intervention wards³. We will adjust for the factor used in stratification (hospitals) as a fixed effect.

Compliance will be analyzed and reported for each occupational group and total for all healthcare personnel. Outbreaks will be analyzed and reported as the number of outbreaks and secondary attack rate per arm, in total and distributed by patients and staff. The incidence of infection in patients will be analyzed and reported in total and by types of infection.

A more detailed description of the analyzes of the main and secondary outcomes will be published in a separate analysis plan.

[figure not shown]

Figure 1. Overview and schedule for the intervention and measurements in the evaluation

Table 2. Dummy table with results for compliance with hand hygiene recommendations

	Intervention arm	Control arm	ICC	Adjusted RR (95% CI)	ARF (95% KI)	p-value
Primary outcome						

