Compliance hand hygiene	540/900 ¹ (0.60)	369/900¹ (0.41)	0.020	1.683 (1.654 – 1.713)	0.279 (0.270-0.288)	<0.05

¹Number of hand hygiene performed by indicated events

Sample size

Sample size calculation (number of wards needed in each arm) is based on the following:

- Type I error rate: 0.05
- Power: 0.80
- Primary outcome is dichotomous with expected baseline proportion: 0.40
- Outcome is measured as simple difference at the end of the intervention period
- Intraclass correlation coefficient (ICC) of primary outcome: 0.10
- Expected number of measured events per cluster (hospital ward): 30
- Degrees of freedom used when adjusting for cluster-level covariates in the analysis: 2
- A priori stratification in the design and analyses
- Hypothesized intervention effect (increased proportion of compliance): 0.20

The estimation of necessary number of wards in both arms is conducted in parallel cluster-randomized trials calculator published by the National Institutes of Health (https://researchmethodsresources.nih.gov/grt-calculator).

Table 3 shows the function of the number of clusters (wards) per arm, and the number of events measured in each ward. The first row shows the number of clusters, while the first column shows the number of events measured per ward. The inner cells show the magnitude of the difference (increase in proportion) that we can identify as significant with a power of 80%. We assume that we

can detect a difference of at least 20%, and the calculations show that we have enough power for this if we have 26 wards in each arm, if there are 30 hand hygiene sessions measured in each ward.

Table 3. Detectable difference in the arms, distributed by number of participating wards per arm and number of events measured per ward

Absolute Detectable Difference Clusters (wards) per arm

		24	25	26	27	28
Events measured per ward	15	0,2266	0,2219	0,2175	0,2134	0,2094
	23	0,2113	0,2069	0,2028	0,199	0,1953
	30	0,2042	0,2	0,1961	0,1923	0,1888
	38	0,1992	0,1951	0,1912	0,1876	0,1841
	45	0,1962	0,1922	0,1884	0,1848	0,1814

Group allocation

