127 There are three general study populations (see above and the study protocol). This SAP introduces a 128 third population not specified in the protocol, hospital ward. This was introduced because one of the 129 secondary outcomes (outbreaks) cannot be measured at the level of employee or inpatient but can 130 be measured at the level of ward.

- 131
- We will exclude hospitals and their associated randomized wards from all analyses if the hospital after randomization decides not to implement or to terminate the execution of NOST, and the decision is communicated to the Norwegian Institute of Public Health.
- 135

136 **4.3 Treatment Allocation**

Stratified randomization will be used to allocate wards to 1:1 intervention and control arms. Randomization will be stratified by hospital. Randomization will be performed using a computer-based system and the investigators will not be able to manipulate treatment allocation. The approach is outlined in the protocol.

141 **4.4 Blinding/Masking**

142 It is not possible to blind trial participants or observers to treatment allocation. While much of the 143 outcome data will be obtained from registries (e.g., to which events are notified), the people who 144 report data may not be blinded to treatment allocation. However, the trial statistician who will analyze 145 the data will be blinded to treatment allocation.

146

147 When all data have been collected, a member of the research group will apply a blind to the treatment 148 allocation variable, so that the statistician will not know which arms correspond to the intervention 149 and control treatments. The analysis of the primary outcome will be performed blinded. Before 150 unblinding, we will publish a short document on Zenodo describing how the result for the primary 151 outcome was interpreted by the project team. The blind will then be removed and the secondary

analyses will be performed unblinded.

153 **5 Outcomes**

154 **5.1 Primary outcome**

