All estimands (see section 9) for which statistical analyses will be performed utilize collapsible measures of effect (risk ratio or mean difference). This allows any non-adherence to be addressed via regression adjustment. We will measure adherence using the proportion of time after randomization and up and including the final data collection period (i.e., adherence will be measured using a value between 0 and 1, inclusive).

294

If 5% or more wards do fully not adhere to their randomized treatment, we will estimate the effect of being randomized and adhering to NOST as the sum (on the log scale for ratio effect measures) of two effects: randomization to NOST and adherence to NOST. Note that adherence to NOST will also be measured in the control arm to facilitate the estimation of the effect of full versus no adherence to NOST. We will then exponentiate the sum to obtain the desired estimate of treatment effect.

300

301 If fewer than 5% of wards do not adhere to their randomized treatment we will not account for the302 non-adherence, but report it is a possible limitation.

303 8 Summary of Study Data

A CONSORT trial flow diagram will be presented.

305

A table of baseline characteristics will be presented following CONSORT guidelines, as follows. Continuous variables will be summarized using the following descriptive statistics: median and interquartile range (IQR). The frequencies and percentages of observed levels will be reported for categorical variables. Baseline characteristics will be reported in a table like the following:

		Control (N = XXX)	NOST (N = XXX)
Hospitals	N (%)	XXX	XXX
Number of beds	Median [IQR]	XXX [XXX to XXX]	XXX [XXX to XXX]
Health region			
North	N (%)	XXX	XXX
Central	N (%)	XXX	XXX
South-East	N (%)	XXX	XXX
Wards	N (%)	XXX	XXX
Health region			

North	N (%)	XXX	XXX
Central	N (%)	XXX	XXX
South-East	N (%)	XXX	XXX
Department			
Oncology	N (%)	XXX	XXX
Orthopedics	N (%)	XXX	XXX
Neurology	N (%)	XXX	XXX
Profession			
Physician	N (%)	XXX	XXX
Nurse	N (%)	XXX	XXX

Effect estimates for the primary and secondary outcomes will be reported in a table like the following:

	Control	Intervention	Risk Ratio (95% Cl)	p -value	Risk Difference (95% Cl)
Primary outcome					
Compliance	XXX/XXX (XXX%)	XXX/XXX (XXX%)	XXX [XXX to XXX]	0.XXX	XXX [XXX to XXX]
Secondary outcomes					
Outbreaks	XXX/XXX (XXX%)	XXX/XXX (XXX%)	XXX [XXX to XXX]	0.XXX	XXX [XXX to XXX]

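### Once 5% or more of wards are non-adherent, every effect estimate is conditioned on post-randomisation adherence, and no comparison by randomised arm is planned beside it

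*SAP*

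**What the plan says.** SAP 3.2 targets the effect of implementing and adhering to NOST and sets aside the effect of a policy of implementing it. SAP 7.6 anticipates that some wards in either arm will depart from their allocation. Adherence is a number from 0 to 1: "We will measure adherence using the proportion of time after randomization". It is measured in control wards too.

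Below 5% non-adherence, SAP 9.1 fits the arm-only model, log p = β0 + βX·x. At 5% or more, "we will estimate the effect of being randomized and adhering to NOST as the sum" of βX and βA, from log p = β0 + βX·x + βA·a. SAP 9.2 does the same for bed-days on the linear scale. The stated ground is collapsibility: "This allows any non-adherence to be addressed via regression adjustment".

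Neither model holds ward-level covariates, and hospital enters only through the standard errors (SAP 7.3). When the sum is used, SAP 9.1.1 adds two sensitivity analyses: a sample restricted to wards that followed their allocation, and the same regression with adherence as a factor. A Wald test of equality of the three estimates is then read as showing whether the result is sensitive to modelling assumptions. SAP 10 lists one adherence-based estimand per outcome. On masking, SAP 4.4 says: "The analysis of the primary outcome will be performed blinded".

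**The concern.** Collapsibility means that conditional and marginal effects agree when there is no confounding. It says nothing about whether wards that start promptly and persist are comparable with wards that do not. Adherence arises after randomisation, so βA rests mainly on an observational comparison among NOST wards, plus any control wards that take NOST up. Adding βA to βX carries that comparison into the headline result.

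Three things follow. The reported effect loses the protection of randomisation. Because the two sensitivity analyses also select or model on adherence, the Wald test can report agreement among estimates that share a bias. And no risk ratio or mean difference by assigned arm, with interval and p-value, is planned above the threshold. The Protocol's own comparison (modified Poisson by arm, under Data collection and outcomes) has no adherence term, but the SAP does not carry it forward in that case.

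**Working it through.** **Inputs from the documents.** Protocol, Sample size: "Primary outcome is dichotomous with expected baseline proportion: 0.40"; ICC 0.10; 30 events per ward; "Hypothesized intervention effect (increased proportion of compliance): 0.20", a planned risk ratio of 0.60/0.40 = 1.5; 26 wards per arm (52 in all). Error rate: "Type I error rate: 0.05", used two-sided. Protocol, Group allocation, expects several hundred wards.

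**The plan's own figure.** From the stated inputs, a standard calculation gives 97 per arm × (1 + 29 × 0.10) / 30 = 97 × 3.9 / 30 = 12.6, so 13 wards per arm (14 with a t-based calculation and 2 df lost), not 26. The difference is on the conservative side, and this point does not depend on it; 52 wards is used below only as the plan's minimum.

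**Assumed.** The documents give neither a non-adherence pattern nor a correlation (rho) between ward engagement and underlying compliance. Both are shown as ranges.

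**How likely is the switch?** 5% of 52 is 2.6, so 3 wards trigger it. If each ward fails independently with probability 5%, the chance of 3 or more is about 49%; with probability 10%, about 90%. The trigger's wording puts 'fully' before the negative, so it can mean total non-adherence or anything short of full adherence. On the second reading a late start counts. Since the clock runs from randomisation, the switch would then be close to certain.

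**What the sum estimates.** Suppose some NOST wards never start (a = 0), the rest adhere fully (a = 1), and no control ward takes NOST up. The three groups have log risks β0 (control), β0 + βX (NOST, never started) and β0 + βX + βA (NOST, adherent). So βX + βA is exactly the log ratio of adherent NOST wards to all controls. The restricted-sample analysis gives the same number, and so does the factor analysis. All three estimates coincide whatever the confounding.

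**Size by hand, no true effect, 20% of NOST wards never starting.**
- Between-ward SD of compliance: √(0.10 × 0.40 × 0.60) = 0.155.
- If engagement is normal, the top 80% average 0.280/0.80 = 0.35 SD above the mean.
- Shift in adherent NOST wards: rho × 0.35 × 0.155 = 0.016 at rho 0.3 and 0.027 at rho 0.5.
- Risk ratio: 0.416/0.40 = 1.04 and 0.427/0.40 = 1.07.
- At 300 wards (120 adherent NOST, 150 control), ward-level variance is 0.24 × 3.9/30 = 0.0312, so SE = √[0.0312 × (1/120 + 1/150)] = 0.0216.
- Shift/SE = 0.75 and 1.25, giving two-sided rejection of about 12% and 24%.

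**Simulation, no true effect.** SAP model, hospital-clustered standard errors. Ranges are across repeated runs; sizes are total wards.

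| Setting | rho | RR from the sum | False positives |
|---|---|---|---|
| 300 wards, 20% of NOST wards never start | 0.3 | 1.04 | 12–13% |
| | 0.5 | 1.07 | 26–28% |
| 300 wards, 20% start late (a 0.6–1), rest a = 1 | 0.3 | 1.03 | 12% |
| | 0.5 | 1.06 | 17–23% |
| 52 wards, 20% start late | 0.3 | 1.03 | 6% |
| | 0.5 | 1.06 | 11% |
| 600 wards, 20% not fully adherent | 0.3 | 1.03 | 14% |
| | 0.5 | 1.06 | 32% |
| Worst case: 300 wards, all NOST wards late (a 0.6–1) | 0.3 | 1.21 | 70–74% |
| | 0.5 | 1.36–1.37 | 99% |

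The arm-only model gave RR 0.99–1.01, with rejection of about 4–8%. At rho = 0, with 10–30% of NOST wards not fully adherent, the sum gave RR 0.99–1.00, with rejection of 4–7%. At 600 wards, 20% non-adherent and rho 0.5, the restricted-sample analysis gave 1.07 (45%) against 1.06 (32%) for the sum: biased the same way.

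**Blinding.** Adherence is near 0 in one arm and near 1 in the other, so the covariate identifies the arms. The analyst also needs to know which arm is NOST to form the estimate: with the arm code reversed, the required contrast is βA − βX.

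**The case against.** The adherence question is deliberate. SAP 3.2 states it, and an arm-only analysis answers a different one. The SAP concedes that its estimator needs a modelling assumption and prespecifies two sensitivity analyses for that reason. SAP 7.2 analyses wards in their randomised arms, and the results table gives raw counts by arm. SAP 9.1 expects most implementing wards to adhere, so a scenario in which every NOST ward starts late is extreme. A bias of 1.03–1.07 is also small against a planned risk ratio of 1.5.

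Much of this stands as a limit on the point. Choosing the estimand is legitimate, but that choice does not validate the estimator. The sensitivity analyses vary the form of the adherence term or restrict on it; none drops the conditioning. Raw counts carry no planned effect estimate, interval or p-value, and analysis by randomised arm does not help when the reported quantity is the sum.

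Stronger readings are tempting but unsupported:
- *The bias favours NOST.* No passage links engagement to underlying compliance. The Protocol presents NOST as revealing areas for improvement, so low-compliance wards might engage more, and the bias would then run the other way.
- *Control wards all have zero adherence.* SAP 7.6 anticipates control-arm uptake and measures it.
- *Only the sum is reported.* The two sensitivity analyses are reported as well.
- *Arm-only would be full intention-to-treat.* SAP 4.2 removes hospitals that decline or stop NOST after randomisation.

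**Conclusion.** The point holds in this form. Above the threshold the plan offers no estimate protected by randomisation, rests its adjustment on a property that does not deal with confounding, and checks it with analyses open to the same bias.

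The size depends on two unstated quantities. With rho 0.3–0.5 and 20% of NOST wards late or never starting, 300 wards give a false risk ratio of about 1.03–1.07 and roughly 12–28% false positives. At 52 wards with 20% non-adherent, false positives are about 6–11%. The 1.21–1.37 range (70–99%) is a worst case that needs every NOST ward to start late; it should not be read as the expected result. With rho = 0 there is no bias, and a negative rho reverses it. Only the primary outcome was simulated; the same structure applies to the secondary outcomes, including the bed-days mean difference, but their bias was not sized. The blinding problem follows from the covariate itself and does not depend on rho.

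**What to change.** 1. For every outcome, report the arm-only model (βX) with confidence interval and p-value beside the adherence estimate, whatever the adherence level. Describe it as a comparison by randomised arm among retained hospitals, because of the exclusions in SAP 4.2.
2. Delete the collapsibility justification. State that βX + βA assumes no unmeasured confounding of adherence and outcome. Keep the implement-and-adhere estimand, and add a sensitivity analysis that uses randomisation as the instrument for a: for example, the arm difference in risk (or in mean bed-days) divided by the arm difference in mean adherence. State its assumptions: assignment acts only through adherence, and a dose-response form.
3. Run the blinded primary analysis with the arm-only model, and release adherence to the analyst only after the blinded interpretation is published.
4. Reword the 5% trigger so that it says whether partial adherence counts.

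Cost: SAP wording, a few lines of code and slightly more to report; no new data. The instrument-based interval is wider than the arm-only one by about 1/(arm difference in mean adherence), for example 1/0.8 = 1.25 times if that difference is 0.8.

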Control	Not implementing NOST				
Primary outcome	Compliance with hand hygiene recommendations by hospital employees who do patient-related work, measured at one year after randomization.				
Design	Cluster-randomized parallel two-arm superiority trial.				
Blinding	Trial participants and other personnel cannot be blinded to treatment allocation. The trial statistician will be blinded to treatment allocation.				
Treatment allocation	Hospital wards will be randomized 1:1. Randomization will be stratified by hospital to ensure approximately equal allocation of wards within hospital.				

99

101

The following table shows the structure of data registered in NOST: 104

1	n	5
т	υ	J

Plac	Place Observation of hand hygiene			2	Person	
Hospital	Ward	Section number	Observation number	Indication	Compliance	Profession
1	5	1	1	А	1	Nurse
			2	В	1	
			3	D	0	
1	4	2	4	В	1	Physician
2	2	3	5	А	0	Nurse
			6	В	1	
			7	С	0	
			8	С	0	
			9	E	1	
1	5	4	10	A	1	Nurse
			11	E	1	assistant

- 107 Description of the variables:
- Hospital: a unique ID-number for each hospital. The data will also include information about
 the actual health trust and health region
- Ward: a unique ID-number for each ward within the actual hospital. The wards will be allocated to intervention and control arms
- Section number: a unique running number for a section of observations where the observer has followed a person and registered all hand hygiene indications happening within a specific setting or task. A section will most often include several observations where the person has or should have performed hand hygiene.
- Observation number: a unique running number for an observation where hand hygiene was
 or should have been performed
- Indication: A code for why hand hygiene was advised, based on the guidelines by the World
 Health Organization
- Compliance: A code displaying whether the person performed hand hygiene or not (1 or 0)
 when the indication arose
- Profession: The health profession of the observed person. Other personal information is not registered. Only one person is observed within a section number, but the same persons may be observed in several sections
- 125

126 4.2 General Study Populations and Inclusion-Exclusion Criteria

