The primary outcome is compliance with hand hygiene recommendations by hospital employees who do patient-related work. Compliance will be assessed one year after randomization by trained and experienced observers. The observers will record the number of observations made and the number of these observations that meet the criteria for compliance. The number of observations and compliances will be measured at the level of hospital ward. Compliance will therefore be aggregated at the level of hospital ward and the primary outcome is a count variable.

161 **5.2 Secondary outcomes**

As for the primary outcome, all secondary outcomes will be aggregated at the level of hospital ward.
Unlike the primary outcome, all secondary outcomes are measured over the one-year trial period
rather than at the end of the trial.

165

Sec	ondary Outcome	Туре	Denominator	Data source			
Infe	Infectious disease outbreaks						
1.	Outbreak	Count	Wards	VESUV			
2.	Inpatient infection	Count	Inpatients in wards with outbreaks				
3.	Employee infection	Count	Employees in wards with outbreaks				
Sur	veillance of HAI						
4.	Inpatient infection	Count	Inpatients included in	NOIS			
			the surveillance				
5.	Inpatient antibiotic treatment	Count	Inpatients included in				
			the surveillance				
Sur	veillance of postoperative site infectior	15					
6.	Inpatient treatment for postoperative	Count	Surgical inpatients	NOIS-POSI			
	site infection		included in the				
			surveillance				
HAI	diagnoses						
7.	Inpatient HAI diagnosis	Count	Inpatients in the study period	NPR			
Len	gth of hospital stay						
8.	Bed-days per inpatient per stay	Continuous		NPR			

166 167

168 6 Sample Size

169 Assuming $\alpha = 0.05$, $\beta = 0.8$, a control risk of 0.4, an intervention risk of 0.6 (i.e., the treatment effect 170 is a risk difference of at least 0.2), an ICC of 0.1, an average cluster size of 30 observations among 171 hospital employees who do patient-related work, a loss of 2 d.f. for adjustment of cluster-level 172 covariates, and stratification by hospital, it was estimated that at least 52 hospital wards should be 173 recruited (26 in each arm).

7 General Analysis Considerations

175 **7.1 Timing of Analyses**

176 Analyses will be performed after the database is locked. No interim or follow-up analyses are planned.

177 7.2 Analysis Sets

Although this SAP defines three populations, there is only a single analysis set that will contain all

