wards randomized and not excluded (see exclusion criteria, above). In practical terms, the data set
will have one ward per row and there will be 9 outcome variables (columns), plus covariates.
Outcomes will be analyzed in the arms to which the wards were randomized.

182 **7.3 Covariates and Subgroups**

183 Because randomization is stratified by hospital, we originally planned to adjust for hospital as a fixed 184 effect in all analyses. However, the planned adjustment would require estimating one parameter for 185 each hospital (minus the reference hospital), in addition to treatment effect. The large number of parameters that would therefore need to be estimated could lead to imprecision on the effect 186 187 estimates and possibly also estimation problems. Further, the trial is unlikely to include all hospitals 188 in Norway and hence the sample will not exhaust all possible levels of the hospital variable. For these 189 reasons, and the chosen regression model (see section 9), we will account for the likely clustering of 190 outcomes within hospital using cluster-robust standard errors, with hospital as the cluster variable.

191

192 We will obtain data on the following variables to support four subgroup analyses:

- 193
- 194 1. Hospital department (e.g., psychiatry, orthopedics, neurology, ...)
- 195 2. Employee profession (e.g., physician, nurse, ...)
- 196 3. Indications of hand hygiene (e.g., before patient contact, after exposure to body fluid,)
- 197

198 These subgroups are based on the hypothesis that baseline hand hygiene compliance may differ by 199 type of ward or type of profession with different levels of education or work tasks, and compliance 200 may vary depending on the situations in which hand hygiene is recommended. It may be the case that 201 treatment effect is different in these subgroups. (For example, if some ward types already have 202 exceptionally high baseline compliance with hand hygiene recommendations, then only a small 203 beneficial treatment effect is possible for this subgroup. Conversely, if a type of ward or profession 204 has exceptionally low baseline compliance for all or some of the indications then a large beneficial 205 treatment effect may be achievable in this subgroup.

206

207 7.4 Multiple Centers

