We will not combine outcomes by ward or hospital (i.e., we will not define "pseudo-centers"). We will not explore treatment-by-hospital interactions. Between-hospital differences in risk of compliance, for example, will be accounted for using cluster-robust standard errors with hospital as the cluster variable.

212 **7.5 Missing Data**

We will examine the data for spurious values and seek to verify or obtain correct values if data are miscoded (e.g., negative counts, nonintegral values entered for counts, or counts that appear to be unrealistically large). We will report any data processing decisions that need to be made at the time of analysis.

217

218 It is very unlikely that data will be missing for the treatment, hospital, or ward variables, which are219 needed in all analyses.

- 220
- 221 Data may be missing for the primary outcome variable, which is measured by observers. It is unlikely

- that data will be missing for the secondary outcome variables, which will be obtained from registries,
 but data will be missing if hospitals do not provide data to the registries (Norwegian Institute of Public
- 224 Health).
- 225

If wards do not provide outcome data for the primary outcome, we will contact them and ask them to provide the missing data. If more than 5% of wards do not provide primary outcome data, we will use Little's test to assess if the data are unlikely to be missing completely at random (MCAR) but missing at random (MAR). If we assess the data to be MAR, we will use multiple imputation by chained equations (MICE) and perform the prespecified analyses including all wards.

231

The primary outcome comprises counts of observations and counts of those observations that meet the criteria for compliance. We anticipate that both counts will be missing for wards that do not provide outcome data. It will therefore be necessary to impute missing values for these variables in a way that ensures both are valid counts, and that the number of compliances is not greater than the number of observations imputed for a given ward. We will do this as follows.

237

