Patients infected	XXX/XXX (XXX%)	XXX/XXX (XXX%)	XXX [XXX to XXX]	0.XXX	XXX [XXX to XXX]
			Mean Difference (95% Cl)	p-value	
Bed days/stay	XXX (SD = XXX)	XXX (SD = XXX)	XXX [XXX to XXX]	0.XXX	

Effect estimates for the subgroup analyses for the primary outcome will be reported in a table like the

following:

3	1	9

	Control	Intervention	Risk Ratio (95% CI)	p -value	Risk Difference (95% Cl)
Department					
Psychiatry	XXX/XXX (XXX%)	XXX/XXX (XXX%)	XXX [XXX to XXX]	0.XXX	XXX [XXX to XXX]
Orthopedics	XXX/XXX (XXX%)	XXX/XXX (XXX%)	XXX [XXX to XXX]	0.XXX	XXX [XXX to XXX]
Neurology	XXX/XXX (XXX%)	XXX/XXX (XXX%)	XXX [XXX to XXX]	0.XXX	XXX [XXX to XXX]
Profession					
Physician	XXX/XXX (XXX%)	XXX/XXX (XXX%)	XXX [XXX to XXX]	0.XXX	XXX [XXX to XXX]
Nurse	XXX/XXX (XXX%)	XXX/XXX (XXX%)	XXX [XXX to XXX]	0.XXX	XXX [XXX to XXX]
Indication					
Before patient	XXX/XXX (XXX%)	XXX/XXX (XXX%)	XXX [XXX to XXX]	0.XXX	XXX [XXX to XXX]
contact					
After exposure to	XXX/XXX (XXX%)	XXX/XXX (XXX%)	XXX [XXX to XXX]	0.XXX	XXX [XXX to XXX]
body fluid					

326 8.1 Derived Variables

The secondary outcomes are derived from ongoing notifications or from reports that hospitals should submit for specific periods, e.g. four times a year. For example, the number of HAIs (NOIS) over the one-year trial period would be the sum of such reports. This has implications for imputation, if some hospitals do not report data for one or more of the four-month periods (see section 7.5).

331 8.2 Protocol Deviations

Any deviations from the original protocol or this SAP will be reported and justified.

333 9 Estimation and Analyses

While this trial is cluster-randomized (ward is the cluster), outcome data will be measured at the level of ward. The unit of randomization and the unit of analysis are therefore identical. It is not necessary to account for cluster randomization as in trials where clusters of units are randomized, and outcomes are measured on the units.

338

339 9.1 Risk Ratio Estimation

If fewer than 5% of wards do not adhere to their randomized treatment, we will estimate marginal
 risk ratios (RRs) using binomial regression without accounting for the non-adherence. For the primary
 and most of the secondary outcomes, this is:

- 343
- 344 345

$$n_i \sim B(N_i, p_i)$$
 where $\log p_i = \beta_0 + \beta_X x_i$

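### The subgroup plan tests each level against no effect and prespecifies no treatment-by-subgroup interaction, and the one-row-per-ward analysis set cannot supply the profession and indication rows

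*SAP*

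**What the plan says.** SAP 7.3 opens with "We will obtain data on the following variables to support four subgroup analyses" and then lists three variables: hospital department, employee profession and hand hygiene indication. The hypothesis it states is that baseline compliance may differ between these groups. It goes on to allow that the "treatment effect is different in these subgroups".

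The output is described in SAP 8: "Effect estimates for the subgroup analyses for the primary outcome will be reported in a table like the" layout that follows. The template has seven level rows (three departments, two professions, two indications). Each row has counts per arm, a risk ratio with interval, a p-value and a risk difference. It has no interaction row or column.

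On data structure, SAP 5.1 says "Compliance will therefore be aggregated at the level of hospital ward and the primary outcome is a count variable". SAP 7.2 defines a single analysis set that "will have one ward per row and there will be 9 outcome variables (columns), plus covariates". SAP 9.1 uses the same layout for its code.

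The source records in SAP 4.1 are finer. Profession is recorded per section ("Only one person is observed within a section number, but the same persons may be observed in several sections"), and each observation carries its own indication code ("Indication: A code for why hand hygiene was advised").

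The only interaction mentioned is in SAP 7.4: "We will not explore treatment-by-hospital interactions".

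**The concern.** Whether an effect differs between subgroups is a question about the contrast between levels. A p-value within one level answers another question, namely whether the effect in that level differs from none. Its size depends heavily on how many wards or observations the level holds. If the planned table is all that is reported, a significant department beside a non-significant one invites a reading of effect modification that the numbers may not support.

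For profession and indication, readers cannot repair this themselves. The level estimates share wards, and the covariance needed to compare them is not in the table.

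Timing matters too. SAP 4.4 has the primary outcome analysed blinded and the secondary analyses run after unblinding, without saying where the subgroup analyses fall. With no model written down, its form could be chosen with results in view.

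**Working it through.** **1. Is there an interaction test anywhere?** SAP 9.1 and 9.2 give models with arm, or arm plus adherence. SAP 9.1.1 varies only how adherence is handled. SAP 10 has no subgroup estimand. SAP 7.4 rules out treatment-by-hospital interactions and is silent on subgroups. The protocol promises results for each occupational group and specifies no comparison of effects. So neither document contains such a test.

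**2. Can the stated data set produce the table?** One primary plus eight secondary outcomes makes the nine outcome columns of SAP 7.2, so no column holds counts by profession or indication. Department is a property of the ward and fits. Profession and indication vary within a ward, so a single ward total cannot be split into physician and nurse rows or into indication rows. The records in SAP 4.1 can be.

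**3. How often would per-level p-values mislead for department?** The documents state no power or error rate for the subgroups, so there is no plan figure to reproduce.

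Inputs from the protocol's Sample size section and SAP 6: control risk 0.40, intervention risk 0.60, ICC 0.10, 30 events per ward, 26 wards per arm, two-sided 0.05. Assumed: three departments of equal size and the same true effect in each.

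- Design effect: 1 + 29 × 0.10 = 3.9
- Variance term: 0.40 × 0.60 + 0.60 × 0.40 = 0.48
- SE within a department: √[0.48 × 3.9 / (30 × 26/3)] = √(1.872/260) = 0.0849
- Power within a department: Φ(0.20/0.0849 − 1.96) = Φ(0.397) = 0.654
- Mixed pattern: 1 − 0.654³ − 0.346³ = 0.68

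On these inputs the overall comparison at 26 wards per arm has power of about 0.98, above the 0.80 that the plan states. If overall power were exactly 0.80, the result would barely change: 2.80/√3 = 1.617, Φ(1.617 − 1.96) = 0.366, and 1 − 0.366³ − 0.634³ = 0.70.

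**4. Simulation.** 600 trials were simulated with 26 hospitals of two wards each, both wards of a hospital in the same department, ICC 0.10, a log-link count model and hospital-clustered standard errors. True risks were 0.40 and 0.60 in every subgroup.

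| Factor (assumed levels) | Mixed or discordant p-values | Interaction test rejects |
|---|---|---|
| Department (3 equal) | 72% | 8% (2 df) |
| Profession (20 and 10 observations per ward) | 10% | 5% |

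The 8% exceeds the nominal 5% because an uncorrected clustered Wald test is anti-conservative with few hospitals.

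**5. Range for department** (formula of step 3, three equal departments, variance term held at 0.48):

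| Wards per arm | True effect | Power per level | Mixed pattern |
|---|---|---|---|
| 26 | 0.20 | 0.654 | 68% |
| 100 | 0.20 | 0.996 | 1.2% |
| 150 | 0.20 | >0.999 | <0.1% |
| 150 | 0.06 (assumed) | 0.397 | 72% |

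**6. Number of tests.** Seven displayed p-values give 1 − 0.95⁷ = 0.30 if independent. They are not, since the three factors re-slice the same observations. The figure is illustrative only.

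**The case against.** The strongest reply has four parts.

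- **Purpose.** The formal hypothesis in SAP 7.3 concerns baseline compliance. A difference in effect is raised only as a possibility, and the plan nowhere says that patterns of significance will be read as effect modification. This stands. A reader might infer that the SAP commits itself to a hypothesis of differing effects; the text does not go that far. But having raised the possibility, the plan gives no valid way to examine it.
- **Feasibility.** A reader might infer that two of the three analyses are impossible. The documents do not support that. The NOST records hold profession and indication, SAP 7.3 says the data will be obtained for this purpose, and the table template implies re-aggregation. What is missing is a statement of the data layout.
- **Size.** The department figure does not carry over to the other two factors. Splitting a ward's 30 events into four sets of 7.5, with the same ICC across levels, leaves (7.5/1.65)/(30/3.9) = 59% of the information in each set, not 25%, and the sets share wards. The protocol's Group allocation section also expects several hundred wards, where at an effect of 0.20 the department problem nearly vanishes. This stands and limits the claim. A reader might also count many more levels than the template shows; 15 to 19 independent tests would give 54% to 62%. The documents show seven rows, and independence fails.
- **Status.** The template is illustrative and does not bar an interaction p-value. True, but nothing in the SAP asks for one, while the per-level p-values are asked for.

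**Conclusion.** The point holds in a limited form. The plan has no valid test of whether effects differ between subgroups, and its stated analysis set does not support two of the three factors. Both follow from the text and need no assumption.

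The size is conditional. For department, a mixed pattern with no true difference would appear in about 70% of trials at 26 wards per arm with three equal departments. It falls to about 1% or less with 100 or more wards per arm and a true effect of 0.20, and returns with a much smaller effect. For two professions it was about 10%.

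The primary estimate, the sample size and the main conclusion are not touched. The change should still be made, because the method written down is a poor one and the standard alternative costs almost nothing.

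**What to change.** Amend SAP 7.3, 8 and 9 before unblinding:

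1. For each factor, fit one log-RR model with arm, subgroup and arm-by-subgroup terms. Report one joint interaction p-value with hospital-clustered standard errors, and name a small-sample correction to apply if hospitals are few.
2. If the adherence model of SAP 9.1 is triggered, say whether its coefficient may also vary by subgroup, because the target effect there is the sum of two coefficients.
3. Keep RR, interval and indicative RD for each level. Drop the per-level p-values.
4. Define ward-by-profession and ward-by-indication rows, built from the NOST observation records. Wards are nested in hospitals, so hospital clustering still covers the repeated rows.
5. Note that an RR interaction can arise from differing baselines alone. For example, a constant difference of 0.20 on assumed baselines of 0.40 and 0.60 gives RRs of 1.50 and 1.33. This matters because differing baselines are the rationale in SAP 7.3.
6. Label the subgroup analyses exploratory.
7. Change the announced number of analyses to three, or name the fourth.

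The cost is SAP wording and a few lines of code. No new data are needed.
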